
 • To assess the proportion of subjects with a response (defined as $\geq 50\%$ improvement in MADRS total score from predose). • To assess the proportion of subjects with remission (defined as MADRS total score ≤ 10). • To define changes in Hamilton Depression Rating Scale (HAM-D). • Generalized Anxiety Disorder 7-Item (GAD-7). • Clinical Global Impression - Severity (CGI-S) and Clinical Global Impression - Improvement (CGI-I). • Quick Inventory of Depressive Symptomatology - 16 Items (QIDS-SR-16). • European Quality - 5 Dimensions - 3 Levels (EQ-5D-3L). • To determine the safety and tolerability of 2 doses of PCN-101 administered IV in subjects with TRD compared with placebo. 	
All secondary efficacy estimands are defined using the same population, ICE strategy, and population level summary (difference in means or proportions between each randomized treatment and placebo, as appropriate) as described above.
 
The variables for the estimands are the following:
 
 • MADRS total score assessed at 2 and 4 hours, 7 and 14 days after the start of the infusion (Days 8 and 15, respectively). Note, for the 2-hour and 4-hour recall periods, the sleep and appetite items are not assessed. • Proportion of subjects with $\geq 50\%$ improvement in MADRS total score at 24 hours, 7 days, and 14 days after start of infusion (Days 8 and 15, respectively). • Proportion of subjects with a MADRS total score ≤ 10 at 24 hours, 7 days, and 14 days after start of infusion (Days 8 and 15, respectively). • Changes in HAM-D on Day 8 and Day 15 after start of infusion. • Change from baseline in GAD-7 by visit. • Change from baseline in CGI-S by visit and CGI-I (calculated from predose CGI-S). • Change from baseline in QIDS-SR-16 by visit. • Change from baseline in EQ-5D-3L by visit. • Safety as assessed by: 
 ◦ Vital signs ◦ 12-lead electrocardiogram (ECG) ◦ Oxygen saturation (SpO_2) ◦ Clinical laboratory parameters

Objectives	Estimands
	
 ○ AEs ○ Modified Observer's Assessment of Alertness/Sedation (MOAA/S) ○ Clinician-Administered Dissociative States Scale (CADSS) ○ Brief Psychiatric Rating Scale - Modified 4 Components (BPRS+) ○ 5-Dimensional Altered States of Consciousness Rating Scale (5D-ASC) ○ Columbia Suicide Severity Rating Scale (C-SSRS).

Overall Design:

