- h. To be collected prior to clinical laboratory assessments. Vital signs will include SBP/DBP, heart rate, respiratory rate, and temperature (tympanic/temporal). Blood pressure and pulse measurements should be taken after the subject has been in a supine or semi-supine position in a rested and calm state for at least 5 minutes. Blood pressure must be recorded using the same arm and position (supine or semi-supine) throughout the study, where possible. Three consecutive blood pressure readings will be recorded at intervals of at least 1 minute and the average of the 3 blood pressure readings will be recorded in the CRF. An abnormal blood pressure value at screening may be repeated once after 10-15 minutes of relaxation to determine the subject's eligibility.
- i. Urine drug screen will be conducted by a local laboratory and include alcohol, ketamine, opiates, cocaine, barbiturates, and/or amphetamine/methamphetamine. Benzodiazepines are allowed up to 6 hours before the start of the infusion, and if needed as rescue medication.
- j. The HAM-D, MADRS, CGI-S, CGI-I, GAD-7, and EQ-5D-3L should be evaluated by a separate Investigator who is not involved with the assessment of safety to avoid functional unblinding.
- k. There are 3 versions of MADRS: 7-day recall, 24-hour recall, and 2-hour recall. For the 2 hour and 4 hour periods, the sleep and appetite items will not be assessed; predose scores for these items obtained on the same day will be carried forward.
- l. The QIDS-SR-14, with a 24 hour recall period, will be used on Visit 2 Day 2 assessment due to recall period.
- m. Note: The predose CGI-S will be used as the basis for calculating the CGI-I at Visit 2.
- n. Note: C-SSRS may be evaluated by either efficacy or safety rater.

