B. Scope of Document

This statistical analysis plan (SAP) is based on the amended version 4.0 of the protocol dated 19May2022. It will govern the analysis of data for this study. The SAP may be modified until the time of database lock for the final analysis. Any deviations from the SAP, including post- treatment unblinding, will be documented as such in the study report. Supportive reference materials include protocol of the study and the accompanying study data collection documents.

II. Protocol Objectives and Analysis Endpoints

The primary, secondary, safety, and exploratory objectives of the current study are shown along with their corresponding endpoints in [Table 1](#).

Table 1 Objectives and Endpoints

Objectives	Endpoints/Estimands
Primary	

To determine the efficacy of 2 doses (30 milligram [mg] and 60 mg) of intravenous (IV) PCN-101 compared with placebo in improving depressive symptoms in subjects with TRD as assessed by change	
MADRS change in total score assessed from baseline (predose) to 24 hours after the start of the infusion of PCN-101.See Section VII.A Primary Estimand for details on estimand definition

from baseline to 24 hours after the start of the infusion of PCN-101 in	
Objectives	Endpoints/Estimands
the Montgomery Åsberg Depression Rating Scale (MADRS) total score.	
Secondary	

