
 To assess the proportion of subjects with a response (defined as $\geq 50\%$ improvement in MADRS total score from predose). To assess the proportion of subjects with remission (defined as MADRS total score ≤ 10). To define changes in Hamilton Depression Rating Scale (HAM-D). To define changes in Generalized Anxiety Disorder 7-Item (GAD-7). To assess Clinical Global Impression - Severity (CGI-S) and Clinical Global Impression - Improvement (CGI-I). To define changes in Quick Inventory of Depressive Symptomatology - 16 Items (QIDSSR-16)*. 	
 MADRS total score assessed at 2 and 4 hours, 7 and 14 days after the start of the infusion (Days 8 and 15, respectively). Note, for the 2 hour and 4 hour recall periods, the sleep items are not assessed, and predose scores for these items obtained on the same day will be carried forward. Proportion of subjects with $\geq 50\%$ improvement in MADRS total score at 24 hours, 7 days and 14 days after start of infusion (Days 8 and 15, respectively). Proportion of subjects with a MADRS total score ≤ 10 at 24 hours, 7 days and 14 days after start of infusion (Days 8 and 15, respectively). Changes in HAM-D on Day 8 and Day 15 after start of infusion. Change from baseline in GAD-7 by visit. Change from baseline in CGI-S by visit and CGI-I (calculated from predose CGI-S). Change from baseline in QIDS-SR-16-by visit*.
Objectives	Endpoints/Estimands

 To define changes in European Quality 5 Dimensions - 3 Levels (EQ 5D-3L). 	
 Change from baseline in EQ 5D-3L by visit.
Safety 
 To determine the safety and tolerability of 2 doses of PCN-101 administered IV in subjects with TRD compared with placebo. 	
 Adverse events (AEs) Columbia Suicide Severity Rating Scale (C-SSRS) Clinical laboratory parameters Vital signs and oxygen saturation (SpO₂) Physical Examination 12-lead electrocardiogram (ECG) Concomitant Therapies Modified Observer's Assessment of Alertness/Sedation (MOAA/S) Clinician Administered Dissociative States Scale (CADSS) Brief Psychiatric Rating Scale - Modified 4 Components (BPRS+) 5-Dimensional Altered States of Consciousness Rating Scale (5D-ASC)

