The primary efficacy endpoint will be based on the change in total MADRS score from baseline at 24 hours after start of infusion.

The MADRS is a ten-item diagnostic questionnaire administered by the study staff to measure the overall severity of depressive symptoms.

The total score is computed as the sum of scores across all 10 items. Higher MADRS score indicates more severe depression. Each item yields a score of 0 to 6, hence the total score ranges from 0 to 60.

$$CMADRS_{total,24hr} = MADRS_{total,24\ hr} - MADRS_{total,Baseline}$$

where

- $CMADRS_{total,24hr}$: Change from baseline in total score MADRS at 24 hours after the start of infusion
- $MADRS_{total,24hr}$: Total score MADRS at 24 hours after the start of infusion

- $MADRS_{total,Baseline}$: Total score MADRS at Baseline

C. Secondary Efficacy Estimand

All secondary efficacy estimands are defined using the same population, intercurrent event strategy, and population level summary (difference in means or proportions between each randomized treatment and placebo, as appropriate) as described in Section VII.A Primary Estimand.

D. Secondary Efficacy Endpoint

Change from baseline in MADRS total score at 2 hours, 4 hours, 7 days, and 14 days after the start of the infusion

The change from baseline MADRS total score will be analyzed for all analysis timepoints.

Since the sleep items will not be assessed at 2 hours and 4 hours after the start of infusion, and the predose scores for these items obtained on the same day will be carried forward.

Proportion of subjects with at least 50% improvement (i.e. reduction) in MADRS total score at 24 hours, 7 days, and 14 days after start of infusion

A subject is considered a responder at a timepoint if a $\geq 50\%$ improvement in MADRS total score (from baseline) is achieved at that timepoint. Any subject who is assessed but not considered as responder at a timepoint will be assumed to be a non-responder at that timepoint.

The proportion of subjects who meet this improvement criterion will be analyzed across different timepoints.

Subjects with MADRS total score ≤ 10 at 24 hours, 7 days, and 14 days after start of infusion will be considered to be in remission

The proportion of subjects who meet this criterion of MADRS total score ≤ 10 will be analyzed across different timepoints. Any subject who is assessed but not considered as remitter at a timepoint will be assumed to be a non-remitter at that timepoint.

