The change from baseline EQ-5D-3L descriptive system and VAS will be analyzed by timepoint.

Change in CGI-S (and CGI-I) score from baseline at 24 hours after start of infusion

The CGI is the general name for two scales: the CGI-S and CGI-I. The CGI-S answers the question "Considering your total clinical experience with this particular case, how ill is the subject at this time?" on a 7-point scale:

- 0 = Not Assessed
- 1 = Normal, not at all ill impaired
- 2 = Borderline ill
- 3 = Mildly ill
- 4 = Moderately ill
- 5 = Markedly ill
- 6 = Severely ill
- 7 = Among the most extremely ill patients

CGI-I answers the question “Compared to her/his condition at admission to the project, how much has he/she changed?” on a 7-point scale and considers the response from the CGIC-S at baseline during the evaluation by the investigator:

- 0 = Not assessed
- 1 = Very much improved
- 2 = Much improved
- 3 = Minimally improved
- 4 = No change
- 5 = Minimally worse
- 6 = Much worse
- 7 = Very much worse

The change from baseline CGI-S scores will be analyzed by timepoint. Since the baseline CGI-S score will be used as a basis in the evaluation of CGI-I by the investigator, the CGI-I is evaluated once during the study.

Change in HAM-D score from baseline by analysis visit

The HAM-D is a 17-item assessment tool pertaining to symptoms of depression experience over the 1 week period prior to assessment.

Classification of symptoms which may be difficult to obtain can be scored as:

- 0 - absent;
- 1 - doubtful or trivial
- 2 - present

Classification of symptoms where more detail can be obtained can be expanded to:

- 0 - absent;

- 1 - mild;
- 2 - moderate;
- 3 - severe;
- 4 - incapacitating.

The HAM-D total score is defined as the summation of scores across the 17 items. Arithmetically, the maximum (most severe) total score would be 52, while the minimum (least severe) total score would be 0.

The change from baseline HAM-D total score will be analyzed by timepoint.

E. Handling of Missing Item Efficacy Endpoint

It is theoretically possible that an individual item score of a questionnaire or assessment scale is left missing, which would lead to an incomplete calculation of the total score. As a result, the following rules will be used to re-calculate total scores if an individual item score(s) is not reported.

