Within a single analysis timepoint per patient, if $\geq 25\%$ of items used to calculate a total score for a given scale are missing, the total scale score for that patient and timepoint will be considered missing.

If $<25\%$ of items are missing, the total score will be calculated (prorated) as the arithmetic mean of non-missing items multiplied by the total expected number of items and rounded up to the nearest integer.

Additionally, separate sensitivity analyses will be performed with missing MADRS data imputed with a multiple imputation method. The multiple imputation (MI) method assumes a missing-at-random (MAR) data missing pattern. Imputation will be performed using the Fully Conditional Specifications parametric regression model. A total of 50 imputations will be generated using PROC MI. For each of the 50 datasets, missing MADRS total score will be imputed using the regression model, as implemented in the PROC MI with the following variables considered (as given on the VAR statement): Treatment, Region, Baseline MADRS and each subsequent post-baseline MADRS score. Response status (Yes, No) and revised change from baseline values will be derived in each MI dataset based on the newly imputed data. The seed to be used in this MI model is 60773.

Example SAS code for PROC MI is as follows:

```
PROC MI DATA=MI NIMPUTE=50 SEED=&SEED. OUT=MI1 ROUND=1 MINIMUM=0;
  CLASS TRTP REGION1;
  VAR TRTP REGION1 ATPTN20 ATPTN40 ATPTN50 ATPTN70 ATPTN80
  ATPTN90;
  FCS REG (ATPTN20 = TRTP REGION1);
```

```
FCS REG (ATPTN40 = TRTP REGION1 ATPTN20) ;
FCS REG (ATPTN50 = TRTP REGION1 ATPTN20 ATPTN40 ) ;
FCS REG (ATPTN70 = TRTP REGION1 ATPTN20 ATPTN40 ATPTN50) ;
FCS REG (ATPTN80 = TRTP REGION1 ATPTN20 ATPTN40 ATPTN50
ATPTN70 ) ;
FCS REG (ATPTN90 = TRTP REGION1 ATPTN20 ATPTN40 ATPTN50
ATPTN70 ATPTN80) ;
RUN;
```

Note: TRTP = randomized treatment group, REGION1 = region (US/Europe). Note: Each of the ATPTNxx variables represent the MADRS score at each analysis timepoint (Pre-dose, 2 hours, 4 hours, 24 hours, Day 8 and Day 15).

The imputation models may be modified based on the actual data if there is an issue in model convergence. If the missingness at the MADRS 24 hour timepoint is >5%, additional analyses exploring missing-not-at-random (MNAR) assumptions will be performed.

F. Primary Efficacy Outcome Analysis

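### Minor: for MADRS at 2 h and 4 h the SAP carries forward only the sleep items, while the protocol carries forward sleep and appetite, so the two scoring rules need aligning

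*SAP*

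**What the plan says.** **Protocol.** Footnote k of the Schedule of Activities (1.3) says that at 2 and 4 hours "the sleep and appetite items will not be assessed; predose scores for these items obtained on the same day will be carried forward". Section 8.1.1 repeats this rule. The list of secondary estimand variables, in the Synopsis and again in Section 3.0 Table 1, says that "the sleep and appetite items are not assessed" at those times, without stating the carry-forward.

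**SAP.** The rule appears twice, each time without appetite. Table 1 (Section II) says that "the sleep items are not assessed, and predose scores for these items obtained on the same day will be carried forward". Section VII.D opens its version with "Since the sleep items will not be assessed at 2 hours and 4 hours after the start of infusion". The SAP mentions no MADRS appetite item anywhere.

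Three other SAP statements bear on how a blank item would be scored:
- VII.B: "The total score is computed as the sum of scores across all 10 items".
- VII.E: if fewer than 25% of a scale's items are missing, "the total score will be calculated (prorated) as the arithmetic mean of non-missing items multiplied by the total expected number of items", rounded up. At 25% or more the total is set to missing.
- V.C.1: baseline values are not to be carried forward.

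**QIDS (a separate item).** For the Day 2 QIDS-SR-14, protocol 8.1.3 omits and carries forward weight and appetite. The SAP (Table 1 footnote and VII.D) carries forward only the weight items.

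**The concern.** Change in MADRS at 2 and 4 hours is a named secondary endpoint for a drug presented as rapidly acting. The total needs ten item scores. If appetite is not rated, as the protocol directs, the SAP does not say what value it takes.

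The two candidate rules behave differently. Carry-forward fixes the appetite change at zero. Proration makes appetite follow the other nine items, which enlarges any early difference between arms. It also compares a prorated post-dose total with a true ten-item baseline. Two competent programmers could therefore produce different 2- and 4-hour totals from the same data.

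**Working it through.** **Does proration apply on a literal reading?** The documents do not list the MADRS items, so I assume one appetite item. One blank item of ten is 10%, below the 25% cut, so VII.E would prorate. (Two blank items would be 20%, still below the cut, with a factor of 10/8 instead of 10/9.) The multiple imputation in VII.E does not fill the gap: it imputes missing total scores, and only as a sensitivity analysis.

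**The two totals.** Let S be the sum of the other nine items, with sleep carried forward (0 to 54, since each item runs 0 to 6), and a0 the predose appetite score (0 to 6).
- Protocol total: S + a0.
- Literal SAP total: 10S/9 rounded up, which equals S + (S/9 rounded up).
- Difference per subject: (S/9 rounded up) − a0. The arithmetic extremes are −6 and +6.

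**One subject, for illustration.** Assume a predose total of 35 and no change in any other item. Carry-forward gives a change of 0. Proration gives:

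| Predose appetite | Nine-item sum | 10S/9, rounded up | Apparent change |
|---|---|---|---|
| 0 | 35 | 39 | +4 |
| 3 | 32 | 36 | +1 |
| 4 | 31 | 35 | 0 |
| 6 | 29 | 33 | −2 |

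**Between-arm difference.** Randomisation balances a0 in expectation and the baseline covariate largely handles chance imbalance. The protocol difference is then the difference D in S. Under proration it is D × 10/9 = 1.111 D, a shift of D/9.
- D = 4 (assumed): 4/9 = 0.44 points.
- D = 8 (assumed): 8/9 = 0.89 points.

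Rounding up adds about 0.44 to 0.45 points in each arm and cancels in the difference. With S modelled as a discretised normal (assumed mean 16 to 30, SD 6 to 11), the ratio of arm differences was 1.110 to 1.111.

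**What does not move.** The estimate and its standard error scale almost together, so tests at 2 and 4 hours hardly change. The 24-hour score is not scored under this rule. The early totals share the MMRM and the imputation model with it, so any effect there is only indirect. SAP VII.D defines response and remission only at 24 hours, 7 days and 14 days.

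**The plan's own figure.** The documents give no expected difference at 2 or 4 hours. Their 8-point planning value is for 24 hours. Its stated 80% power reproduces (80.4% by the exact t calculation with 31 per arm and SD 11), but nothing here depends on it.

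**QIDS item count.** A 14-item form implies 16 − 14 = 2 omitted items. Protocol 8.1.3 assigns appetite and weight to Questions 6 to 9, which is four items. The SAP's two weight items fit the name.

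**The case against.** The strongest reply is that the SAP is silent on appetite and directs no different score. It lists the protocol among its references: "Supportive reference materials include protocol of the study and the accompanying study data collection documents". The protocol states an explicit rule, so a programmer would naturally apply it. VII.E is also introduced for accidents: "It is theoretically possible that an individual item score of a questionnaire or assessment scale is left missing". An item omitted by design, with a value specified in the protocol, is not that case. The carry-forward may already be built into the form, and the forms are not part of these documents. The V.C.1 sentence cannot be absolute either, since the SAP itself carries the sleep items forward.

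Most of this stands, and it makes the scoring consequence conditional. It does not remove the mismatch. SAP I.B makes the SAP the controlling document for the analysis and requires deviations from it to be documented. The proration rule is triggered whenever an item score is not reported, whatever its introduction suggests.

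A reader might go further and infer that the SAP mandates proration, so that the early effect will be reported about 11% too large. The documents do not support that: they do not show that a blank appetite item reaches the analysis, and proration is not the most natural reading. Nor do they support an inference that significance at 2 or 4 hours, or the 24-hour result, would be inflated. Setting the shift against a fixed standard error would suggest this wrongly, because the standard error grows with the estimate.

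**Conclusion.** The SAP is wrong as written, and the matter is minor. The disagreement between the documents is certain. Its effect is zero if appetite was rated, pre-filled, or scored by the protocol rule. If one appetite item was left blank and prorated, the 2- and 4-hour differences would be multiplied by about 10/9. Only the size of those secondary estimates is at stake. High confidence attaches to the mismatch in wording, not to the scoring consequence, which depends on forms and programming that the documents do not show.

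The QIDS discrepancy is a separate reconciliation and lends no weight to the MADRS point. There the SAP fits the 14-item name better than protocol 8.1.3 does.

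**What to change.** Before unblinding, check whether the 2-hour MADRS form rated appetite.
- **If it did not:** state in SAP Table 1 and VII.D that both the sleep and the appetite items take their same-day predose scores at 2 and 4 hours. Add that VII.E proration and the V.C.1 sentence do not apply to items omitted by design.
- **If it did:** correct the protocol text (Synopsis, 1.3 footnote k, Section 3.0 Table 1 and 8.1.1) and document the correction.

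Separately, make protocol 8.1.3 and the SAP name the same omitted items for the Day 2 QIDS-SR-14, checked against the form used.

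The cost is a few words in the SAP and one clarification for the QIDS, with no effect on data collection or patients.

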8.1.2 Hamilton Depression Rating Scale

The Hamilton Depression Rating Scale is a 17-item questionnaire designed to assess a subject’s level of depression before, during, and after treatment. The survey is used as a guide to evaluate recovery and is based on the clinician’s interview with the subject. The HAM-D rates the severity of depression by probing mood, feelings of guilt, suicide ideation, insomnia, agitation or retardation, anxiety, weight loss, and somatic symptoms. Scoring take about 15 minutes. The rater enters a number for each symptom that ranges from 0 (not present) to 4 (extreme symptoms). During this study, the questionnaire will be completed at screening, baseline, predose on Day 1, at Day 2 discharge, and both follow-up visits.

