Change in QIDS-SR-16 score from baseline by analysis visit

The QIDS-SR-16 is a 16-item self-assessed questionnaire which measures depression symptoms. Each item contributes a score of 0 to 3.

Item #6 and #7 measures decreased and increased appetite respectively, hence at least 1 of these 2 items should be reported as 0. Similarly, item #8 and #9 measures

decreased and increased weights respectively, hence at least 1 of these 2 items should be reported as 0.

An abbreviated version (ie, QIDS-SDR-14) is only done once at Visit 2 'discharge' timepoint. For this timepoint, the decreased/increased weight items score from Day 1 predose will be carried forward to Visit 2 in the calculation of the total score at Visit 2 'discharge'.

As a result, arithmetically, the maximum (most symptomatic) total score would be 42, while the minimum (least symptomatic) total score would be 0.

The change from baseline QIDS-SR-16 score will be analyzed by timepoint.

Change in GAD-7 score from baseline by analysis visit

The GAD-7 is an initial screening tool for generalized anxiety disorder. It consists of 7 questions pertaining to the different anxiety disorder problems over a 2 week period prior to the assessment. Each item contributes a score 0 to 3, where a score of 0 indicates 'Not at all' and 3 indicates 'Nearly every day' for each of the 7 items.

The GAD-7 total score defined as the summation of scores across all questions. Arithmetically, the maximum (most anxiety) total score would be 21, while the minimum (no anxiety) total score would be 0.

The change from baseline GAD-7 score will be analyzed by timepoint.

Change in EQ-5D-3L index from baseline by analysis visit

The EQ-5D-3L is a questionnaire that essentially consists of 2 pages - the EQ-5D descriptive system and a visual analog scale (VAS). The descriptive system is comprised of 5 dimensions: mobility, self-care, usual activities, pain/discomfort, and anxiety/depression. Each dimension has 3 levels: no problems, some problems, and extreme problems. The subject will be asked to indicate his/her health state by marking the box for the most appropriate statement in each of the 5 dimensions. The VAS records the subject's self-rated health on a vertical VAS where the endpoints are labeled "best imaginable health state" and "worst imaginable health state." This information will be used as a quantitative measure of health outcome.

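### The SAP's single item-proration rule can misstate HAM-D totals in either direction, inflates QIDS totals if a paired item is left blank, and always rounds up

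*SAP*

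**What the plan says.** SAP VII.E (Handling of Missing Item Efficacy Endpoint) treats a total as missing when 25% or more "of items used to calculate a total score for a given scale are missing". Below that threshold the total is "the arithmetic mean of non-missing items multiplied by the total expected number of items and rounded up to the nearest integer". No scale has its own version, and totals are not capped at the scale maximum.

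SAP VII.D describes the scales to which this applies:

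- **HAM-D:** "The HAM-D total score is defined as the summation of scores across the 17 items". One group of items is scored 0–2 ("Classification of symptoms which may be difficult to obtain can be scored as") and another 0–4 ("Classification of symptoms where more detail can be obtained can be expanded to"). "Arithmetically, the maximum (most severe) total score would be 52".
- **QIDS-SR-16:** items are scored 0–3. Items 6/7 (appetite) and 8/9 (weight) are opposite pairs, "hence at least 1 of these 2 items should be reported as 0". The stated maximum is 42.
- **MADRS:** ten items, each 0–6, total 0–60.
- **GAD-7:** seven items, each 0–3, total 0–21.

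Protocol 8.1.2 describes HAM-D differently: "The rater enters a number for each symptom that ranges from 0 (not present) to 4 (extreme symptoms").

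For MADRS at 2 h and 4 h, the protocol (8.1.1 and Schedule of Activities footnote k) leaves both sleep and appetite unassessed and carries their predose scores forward. The SAP (Table 1 and VII.D) mentions sleep only.

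**The concern.** Multiplying the mean of the observed items by the item count is sound only if all items share one range and can vary independently. MADRS and GAD-7 have a common item range. HAM-D, as the SAP scores it, does not, so the prorated total depends on which type of item is missing. QIDS has two structural zeros. If such an item is blank, the rule fills it with the average of the other items.

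Rounding up is a separate matter. It can only raise a prorated value or leave it alone, so the error does not average out over subjects as rounding to nearest roughly would.

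At stake are totals above the scale's own maximum on two secondary endpoints, and an occasional change of MADRS response status.

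**Working it through.** **The plan's own maxima.** For HAM-D, let a items be scored 0–4 and b items 0–2. Then a + b = 17 and 4a + 2b = 52 give a = 9 and b = 8, the only solution, so 52 is reproduced. For QIDS, (16 − 2) × 3 = 42 is reproduced.

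**When the rule applies.** Fewer than 25% missing means at most 2 of 10 MADRS items, 4 of 17 HAM-D items, 3 of 16 QIDS items and 1 of 7 GAD-7 items.

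**HAM-D.** The prorated total is the ceiling of S × 17/(17 − k), where S is the observed sum and k the number of missing items.

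| k missing | True 52, 0–2 items missing | True 52, 0–4 items missing | True 26, 0–2 items missing | True 26, 0–4 items missing |
|---|---|---|---|---|
| 1 | 50 × 17/16 = 53.1 → 54 | 48 × 17/16 = 51.0 → 51 | 27 | 26 |
| 2 | 48 × 17/15 = 54.4 → 55 | 44 × 17/15 = 49.9 → 50 | 28 | 25 |
| 3 | 46 × 17/14 = 55.9 → 56 | 40 × 17/14 = 48.6 → 49 | 28 | 25 |
| 4 | 44 × 17/13 = 57.5 → 58 | 36 × 17/13 = 47.1 → 48 | 29 | 24 |

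The true 26 has every item at half its range. Before rounding, the relative error for items at a uniform fraction of range is +2.2% (one 0–2 item) to +10.7% (four), or −1.9% (one 0–4 item) to −9.5% (four). Rounding to nearest does not remove the problem: one missing 0–2 item still gives 53.

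**QIDS, non-applicable pair member blank.** With both pairs affected, 14 items are observed:

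- True 20: 20 × 16/14 = 22.9 → 23.
- True 42: 42 × 16/14 = 48.

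With one pair affected, a true 42 gives 42 × 16/15 = 44.8 → 45. If three other items are missing instead, the structural zeros pull the mean down: 33 × 16/13 = 40.6 → 41 for a true 42.

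**Rounding up, MADRS.** Take observed sums spread evenly over a full cycle.

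- One item missing: the excess takes the values 0, 1/9, …, 8/9, so the mean is 36/81 = 0.44 and the maximum 0.89.
- Two missing: the excess takes the values 0, 0.25, 0.50, 0.75, so the mean is 0.375.

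**Response.** Take baseline 23 and nine items summing to 10. The prorated value is 10 × 10/9 = 11.1, an improvement of (23 − 11.1)/23 = 51.7%, which is a response. Rounded up to 12, the improvement is (23 − 12)/23 = 47.8%, which is not. Rounding to nearest (11) keeps the response.

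**Remission.** The cut-off is the integer 10, so a value at or below 10 stays there when rounded up, and a value above 10 was already above it. Status does not change.

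**Primary contrast.** Assume 1% to 10% of 24-hour scores in an arm have one prorated item (the documents give no rate). The arm mean moves by 0.01 × 0.44 = 0.004 to 0.10 × 0.44 = 0.044 points, against a design difference of 8. Similar rates across arms largely cancel even this.

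**How often the rule could apply at 2 h and 4 h.** Under the SAP text, sleep is carried forward but appetite is not. If appetite is unassessed, as the protocol says, 1 of 10 items (10%) is missing from every total. Each is then prorated and rounded up, by about 0.44 points on average in every arm.

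**The case against.** The SAP calls a missing item only theoretically possible, expects little missing data while subjects are in the clinic, and applies the same rule to all arms. A total of 58 out of 52 needs every observed item at maximum and four missing items all of the 0–2 type. Exceeding 52 at all needs an observed sum of at least 49 of 50 (one 0–2 item missing) or 40 of 44 (four missing). The QIDS case needs a blank where the SAP expects a 0. HAM-D has no model in SAP VII.H, VII.I or Table 3, although Protocol 9.4.2 plans one. On the protocol's HAM-D description every item is 0–4, the maximum would be 17 × 4 = 68, and the unequal-range problem disappears.

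Most of this stands as a limit on size. It does not make the rule right: the true-26 rows show errors at ordinary severity, and the HAM-D conflict itself has to be settled.

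A reader might infer two stronger conclusions, which the documents do not support.

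- **That every prorated score is biased towards worse.** Rounding adds nothing when the product is an integer. HAM-D is too low when 0–4 items are missing. A MADRS with nine items at 2 and a missing item of 6 returns 20 for a true 24.
- **That improvement is therefore understated.** This needs complete baseline forms, which the documents do not state. The rule covers any timepoint, and a baseline rounded up makes improvement look larger.

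**Conclusion.** The rule is wrong as written for HAM-D under the SAP's scoring: it can return totals above 52 and can misstate totals in either direction. For QIDS the inflation is conditional on a non-applicable pair member being left blank. Rounding up adds an avoidable one-directional error below one point, which matters only for response near the 50% boundary. The primary MADRS contrast is not at risk if item missingness is rare and similar across arms.

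The HAM-D result rests on the SAP maximum of 52. The average rounding figures rest on observed sums being evenly spread, and the arm-mean shift on an assumed 1% to 10% of scores being prorated.

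**What to change.** Replace the rule in SAP VII.E as follows.

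1. Prorated total = observed sum × (scale maximum / maximum possible on the observed items). This returns 52 and 26 in all the HAM-D cases above and cannot exceed the scale maximum. For MADRS and GAD-7 it equals the present rule before rounding.
2. Keep the unrounded value, or round to nearest if an integer is needed.
3. For QIDS pairs 6/7 and 8/9, set a blank member to 0 when its partner is answered, before counting missing items. Count each pair as one 0–3 component in the maximum.

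Three pieces of text also need attention.

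- Reconcile the HAM-D item ranges in Protocol 8.1.2 with the maximum of 52 in SAP VII.D.
- Reconcile the MADRS items carried forward at 2 h and 4 h (protocol: sleep and appetite; SAP: sleep only). The Day 2 QIDS has a similar mismatch: weight and appetite in Protocol 8.1.3, weight only in SAP VII.D.
- State whether item proration falls under the SAP's statements that missing data are not imputed (V.C.1, VII.F, VII.H).

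The cost is SAP wording and one derivation line per scale. No new data are needed, and SAP I.B allows changes until database lock.
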